5.4.2 Adverse Events

AE collection will begin from the time of informed consent and continue through 30 days after last dose. See **Section 5.5 Adverse Events and Other Safety Aspects** for information regarding adverse event collection and data handling.

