7.9 Handling of Missing Data, Outliers, Visit Windows, and Other Information

As a general principle, no imputation of missing data will be done. Exceptions are the start and stop dates of AEs and concomitant medication. The imputed dates will be used to determine whether a medication was given concomitantly and whether an AE is/is not treatment emergent. Listings of the AEs and concomitant medications will present the actual partial dates; imputed dates will not be shown.

See the SAP for details of the definitions for windows to be used for analyses by visit.

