- j The window for all radiological assessments is ± 7 days. At Weeks 9, 17, 25 and subsequent assessments prior to treatment discontinuation, all other procedures must be completed within the ± 3 day window. Bone progression at the first reassessment at Week 9 requires a confirmatory scan 6 or more weeks later.
- k Adverse events, serious or non-serious, will be collected from the time the patient signs the consent form until the Safety Follow-Up visit, regardless of initiation of another anti-neoplastic therapy prior to last dose of enzalutamide.
- l Long-term follow-up for radiographic progressions (until progression or initiation of new anti-neoplastic therapy), survival, and subsequent anticancer therapies should be performed every 12 weeks for a maximum of 3 years from first dose. The study will end when the last subject has been followed for 1 year from date of first dose.
- m Enzalutamide will be administered until the disease progression, including radiographic progression or unequivocal clinical progression. Per the Investigator's clinical judgment and with sponsor approval, patients may be allowed to continue enzalutamide until the next treatment is initiated. If another non-cytotoxic, non-investigational, antineoplastic agent is initiated after protocol-defined progression has been determined, enzalutamide may be continued per the Investigator's clinical judgment and with sponsor approval as long as the patient is tolerating enzalutamide and continues androgen deprivation therapy
- n Blood samples for CTC molecular profiling and serum samples will be collected at baseline, week 13, time of PSA progression, and time of radiographic progression.

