6.2 Safety Variables

Safety will be assessed by evaluation of the following variables:

- Treatment-emergent adverse events (TEAEs; frequency, severity, seriousness, and relationship to study drug).
- Clinical laboratory variables (hematology, biochemistry including liver enzymes and total bilirubin, and urinalysis)
- Vital signs (systolic and diastolic blood pressure and pulse rate)
- ECOG PS

TEAE is defined as an adverse event observed after first dose of study medication. All adverse events collected that begin within 7 days after taking the last dose of study drug will also be counted as TEAE. Any AE with missing onset date will be considered as TEAE, unless the year and month are prior to the first dose of study medication.

A drug-related TEAE is defined as any TEAE with at least possible relationship to study treatment as assessed by the investigator or with missing assessment of the causal relationship.

Serious adverse events (SAEs) include adverse events that are flagged as serious by the investigator on eCRF, or upgraded by the Sponsor based on review of the Sponsor's list of Always Serious term.

The adverse events will be coded by body system using a MedDRA® dictionary. The severity of adverse event will be graded by NCI CTCAE Grade.

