7.5.1 Adverse Events

An overview table will include the following details:

- Number of TEAEs,
- Number and percentage of subjects with TEAEs,
- Number of drug related TEAEs,
- Number and percentage of subjects with causally drug related TEAEs,
- Number of serious TEAEs,
- Number and percentage of subjects with serious TEAEs,
- Number of serious drug related TEAEs,
- Number and percentage of subjects with serious drug related TEAEs,
- Number of TEAEs leading to permanent discontinuation of study drug,
- Number and percentage of subjects with TEAEs leading to permanent discontinuation of study drug, and
- Number of deaths.

The number and percentage of subjects with TEAEs, as classified by SOC and PT will be summarized. Summaries will be provided for:

- TEAEs,
- TEAEs by NCI CTCAE grade
- drug related TEAEs,
- serious TEAEs,
- serious TEAE by NCI CTCAE grade
- drug related serious TEAEs,
- drug related serious TEAEs by NCI CTCAE grade
- TEAEs leading to permanent discontinuation of study drug,
- drug related TEAEs leading to permanent discontinuation of study drug,
- TEAEs excluding serious adverse events that equal to or exceed a threshold of 5.0%, and
- common TEAEs that equal to or exceed a threshold of 5.0 %.

The number and percentage of subjects with TEAEs, as classified by PT only, will be summarized in descending frequency.

The number of TEAEs and the number and percentage of subjects with TEAEs, as classified by SOC and PT will also be summarized by NCI CTCAE grade to study drug. In the subject count, if a subject has multiple TEAEs with the same SOC or PT, but with differing severity, then the subject will be counted only once with the worst severity, however, if any of the severity values are missing then the subject will be counted only once with missing severity. In the adverse event count, the adverse events will be presented in each category they were classified to. Drug related TEAEs will be presented in a similar way by severity only.

TEAEs of special interest will be summarized by the number and percentage of subjects with the following AEs: fatigue, fall, hypertension, non-pathological fractures, cognitive/memory impairment, loss of consciousness, neutropenia, and convulsion.

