7.11 Handling of Missing Data, Outliers, Visit Windows, and Other Information

Refer to the data specification document in which more details are provided.

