7.11.1 Missing Data

As a general principle, no imputation of missing data for other variables will be done. Exceptions are the start and stop dates of AEs and concomitant medication. If day is missing from any date in a derivation then calculate the derived value using 15th day of month. If month or year is missing from any date in a derivation then set the derived value to missing.

Adverse events with missing relationship will be summarized as 'Related to Study Drug'. Adverse events with missing severity grade will be handled as 'missing'.

Incomplete onset dates default AEs to treatment emergent. Listings of the AEs and concomitant medications will present the actual partial dates; imputed dates will not be shown.

Cases where the onset date of an AE is (partially) missing, will be addressed prior to or during the DRM in order to determine whether the AE must be considered treatment emergent or not.

Imputation on missing date of initial diagnosis (cancer duration) and cancer treatment history (start date, stop date, or date of procedure) will be done as follows:

- Incomplete Day: use the 15th day of the month
- Incomplete Month: use 1st of July if the Year is before Year of dosing, otherwise missing.
- Incomplete Year: no imputation, the derived variable is considered to be missing.

Imputation methods will not be used to determine other endpoints.

Listings will always show the original date information without imputation, but derived parameters (TEAE indicator, start day, end day, study day) will be flagged.

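### SAP 6.2 does not say when the treatment-emergent period ends; if its 7-day sentence is the cut-off, AEs collected from day 8 after the last dose drop out of the TEAE tables

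*SAP*

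**What the plan says.** SAP 6.2 opens with "TEAE is defined as an adverse event observed after first dose of study medication". It gives no end to the period. The next sentence is "All adverse events collected that begin within 7 days after taking the last dose of study drug will also be counted as TEAE". The same section makes a drug-related TEAE a subset of TEAEs.

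SAP 7.5.1 builds its AE tables on that flag: "The number and percentage of subjects with TEAEs, as classified by SOC and PT will be summarized", followed by serious, drug-related, by-grade, discontinuation and special-interest versions.

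On collection, protocol 5.4.2 states "AE collection will begin from the time of informed consent and continue through 30 days after last dose". SAP section 2, note k, says AEs "will be collected from the time the patient signs the consent form until the Safety Follow-Up visit"; the protocol's own schedule carries the same note. That visit is set about 30 days after the last dose with a ±7-day window, or before new anticancer therapy if that comes first.

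Protocol 7.5.1 plans summaries of AEs, SAEs, AEs leading to discontinuation and related AEs, does not restrict them to TEAEs, and lists every AE.

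**The concern.** The two sentences in SAP 6.2 do not fit together. If the first is open-ended, the second adds nothing. If the second is meant to do something, the first must cover only the time on treatment, and the period closes at last dose plus 7 days. A programmer who takes the 7-day rule as the cut-off gets different tables from one who takes the first sentence literally, and both can point to the text.

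Safety is a secondary objective. On the 7-day reading, a serious event that the investigator considers related and that starts on day 10 would be missing from both the serious and the drug-related tables. The laboratory shift tables in SAP 7.5.2 use the worst post-baseline grade with no 7-day limit, and laboratory tests are drawn at the Safety Follow-Up visit. A late abnormality could therefore enter the laboratory tables while the matching AE is absent from the TEAE tables.

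The literal reading is not tidy either. Protocol 5.5.8 asks for new SAEs found during AE follow-up to be reported, and with no stated end any such event in the database would count as treatment-emergent.

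**Working it through.** The plan gives no figure to reproduce. The check compares the text and counts days.

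**Step 1: does another section supply the end date?**
- Protocol 7.9 uses imputed dates to decide "whether an AE is/is not treatment emergent" but gives no window.
- SAP 7.5.1 uses the TEAE flag and gives no window.
- SAP 7.11.1 defaults incomplete onset dates to treatment-emergent, then says partly missing ones "will be addressed prior to or during the DRM in order to determine whether the AE must be considered treatment emergent or not". It gives that review no end date to apply.
- SAP 7.11 says "Refer to the data specification document in which more details are provided". That document is not among those available, so it may hold the answer, but the SAP does not.

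No section available settles the point.

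**Step 2: the two readings**

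| Reading | Role of the 7-day sentence | Collected post-dose days excluded |
|---|---|---|
| Literal: any AE after first dose | Redundant clarification | 0 |
| 7 days closes the period | Sets the cut-off | Day 8 to end of collection |

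**Step 3: days excluded on the second reading**

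Let E be the last day of AE collection, counted from the last dose. Days excluded = max(0, E − 7); share of post-dose collection days = (E − 7)/E.
- E = 30 (protocol 5.4.2, or a visit exactly on schedule): 30 − 7 = 23; 23/30 = 77%.
- E = 23 (note k governs, visit at the early edge of the window): 23 − 7 = 16; 16/23 = 70%.
- E = 37 (note k governs, visit at the late edge): 37 − 7 = 30; 30/37 = 81%.
- E of 7 or less (note k governs, visit brought forward for new therapy): 0.

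These are shares of days. The documents give no AE rate after the last dose, so they cannot be turned into numbers of events.

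**Step 4: which AEs are exposed**

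Only those with a known onset date. SAP 6.2 counts an AE with a missing onset date as a TEAE unless its year and month precede first dose, and SAP 7.11.1 sets the same default for incomplete dates.

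**Step 5: is 7 days explained?**

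The documents give no reason. For context only, protocol 1.2 states a mean terminal half-life of 5.8 days. Assuming first-order decline of the parent drug and ignoring the active metabolite, the fraction remaining is 0.5^(t/5.8):
- t = 7: 0.5^1.21 = 0.43.
- t = 30: 0.5^5.17 = 0.03.

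No document makes washout the criterion for the window, so this shows only that 7 days is not self-explanatory.

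**The case against.** The strongest reply is that the text excludes nothing. The opening sentence is complete by itself, and the 7-day sentence is worded to include events. It could be a redundant reminder that onset after stopping still counts. That stands: this is an ambiguity, not a proven exclusion. A reader might infer that the SAP drops all AEs from day 8, but the wording does not say so.

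A reader might also infer that these events would vanish from the trial's reporting. The documents do not support that. Protocol 7.5.1 lists every AE and plans summaries with no TEAE limit. The count of deaths in the SAP 7.5.1 overview is not tied to TEAEs, and incomplete onset dates default to TEAE. These safeguards limit the effect to the SAP's TEAE tables. The unrestricted protocol summaries also work the other way, because on the 7-day reading the SAP would be narrower than the protocol without saying so.

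Third, the length of the window is a choice. Treatment generally continues until progression, and protocol 5.5.2 collects symptoms of progression as AEs, so a longer window brings disease-related events into the tables of a study with no control arm. That is a fair reason someone might give for a short window, but neither document gives it. The lack of a stated reason does not make 7 days wrong.

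Finally, the data specification document may already fix the window. If so, SAP 6.2 should still say what it is.

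**Conclusion.** SAP 6.2 leaves the end of the TEAE period unstated, and its 7-day sentence has a practical effect only as a cut-off. If it is applied that way, AEs with known onset from day 8 to the end of collection leave all the TEAE tables in SAP 7.5.1. The loss is up to 23 of 30 post-dose collection days, 16 of 23 to 30 of 37 across the visit window, and fewer or none if the visit is brought forward. That would be out of line with the 30-day collection in protocol 5.4.2 and with the unrestricted summaries in protocol 7.5.1.

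The size depends on two assumptions: that the 7-day reading is the one programmed, and which of the two statements ends collection. The number of events affected cannot be computed. Severity is minor to moderate, because the data are collected and listed in any case but the main safety tables depend on the answer.

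**What to change.** Preferred change, in SAP 6.2: define the TEAE period as first dose through the end of AE collection. State whether 30 days after the last dose or the Safety Follow-Up visit governs, and flag AEs that begin after new anticancer therapy.

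Alternative: keep 7 days, say explicitly that it closes the period, give the reason, and add one table of AEs and SAEs from day 8 to the end of collection.

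Either way, apply the same end date when partly missing onset dates are reviewed under SAP 7.11.1, and settle it before database hard lock, since the study is open-label.

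The cost is a short text edit plus one flag, or one extra table. No new data are needed. The downside of the preferred change is that some progression symptoms will enter the tables of a single-arm study; the new-therapy flag identifies later onsets but does not remove these.

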^b Or before the initiation of another systemic antineoplastic therapy, whichever comes first. AE and clinical lab assessments will be performed during the Safety Follow-Up visit, regardless of initiation of another antineoplastic therapy prior to last dose of enzalutamide.

^c A brief physical examination is required at each study visit, with the exception of the Screening visit during which a complete physical examination will be completed.

Sponsor: APGD, Medical Affairs, Americas

ISN/Protocol 9785-MA-1008

- CONFIDENTIAL -

- ^e A MUGA scan or echocardiogram is required if the patient has a history of anthracycline treatment, or if the subject has congestive heart failure New York Heart Association (NYHA) class 3 or 4.
- ^f Laboratory assessments include serum chemistries and hematology.
- ^g Collect a blood sample for additional safety testing if indicated.
- ^hPSA progression, defined as a \geq 25% increase and an absolute increase of \geq 2 μg/L (2 ng/mL) above the nadir, needs to be confirmed by a second consecutive value obtained 3 or more weeks later.
- The window for all radiological assessments is \pm 7 days. At Weeks 9, 17, 25 and subsequent assessments prior to treatment discontinuation, all other procedures must be completed within the \pm 3 day window. Bone progression at the first reassessment at Week 9 requires a confirmatory scan 6 or more weeks later.
- ^jAdverse events, serious or non-serious, will be collected from the time the patient signs the consent form until the Safety Follow-Up visit, regardless of initiation of another anti-neoplastic therapy prior to last dose of enzalutamide.
- ^k Long-term follow-up for radiographic progressions (until progression or initiation of new anti-neoplastic therapy), survival, and subsequent anticancer therapies should be performed every 12 weeks for a maximum of 3 years from first dose. The study will end when the last subject has been followed for 1 year from date of first dose.

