5.1.5 Criteria for Continuation of Treatment

Subjects will receive treatment until the time of disease progression, including radiographic or unequivocal clinical progression, or unacceptable toxicity. Per the Investigator's clinical judgment and with sponsor approval, patients are allowed to continue study drug until next treatment is initiated. If another non-cytotoxic, non-investigational, antineoplastic agent is

initiated after protocol-defined progression has been determined, study drug therapy may be continued per the Investigator's clinical judgment and with sponsor approval as long as the patient is tolerating the study drug and continues androgen deprivation therapy.

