5.5.2 Disease Progression

It is anticipated that a proportion of subjects will experience disease progression. Disease progression should not be reported as an adverse event. Clinical signs and symptoms due to disease progression will be collected as AEs. Individual signs and symptoms will be listed rather than the term "disease progression" with the following exception: if disease progression is the cause of death, this event may be recorded as an AE with "metastatic prostate cancer disease progression" as the reported term.

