5.5.5 Criteria for Causal Relationship to the Study Drug

Adverse events that fall under either "Possible" or "Probable" should be defined as "adverse events whose relationship to the study drugs could not be ruled out".

Causal relationship	Criteria for causal relationship
to the study drug	
Not Related	A clinical event, including laboratory test abnormality, with a
	temporal relationship to drug administration which makes a causal
	relationship improbable, and/or in which other drugs, chemicals or
	underlying disease provide plausible explanations.
Possible	A clinical event, including laboratory test abnormality, with a
	reasonable time sequence to administration of the drug, but which
	could also be explained by concurrent disease or other drugs or
	chemicals. Information on drug withdrawal may be lacking or
	unclear.
Probable A clinical event, including laboratory test abnormality, with	
	reasonable time sequence to administration of the drug, unlikely to
	be attributed to concurrent disease or other drugs or chemicals, and
	which follows a clinically reasonable response on re- administration
	(rechallenge) or withdrawal (dechallenge).

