3.2 Study Design

This is a US-based, multicenter, open-label, single-arm, study evaluating the efficacy, safety, and tolerability of open-label enzalutamide in the re-treatment setting. A total of 40 patients will be enrolled. Patients must have been previously treated with enzalutamide in the pre-chemotherapy setting for a minimum of 8 months, followed by docetaxel for a minimum of 6 cycles. Exposure to intervening systemic anti-cancer therapies such as abiraterone prior to docetaxel is allowed. Subjects will receive treatment with open-label enzalutamide (160 mg daily), administered as four 40 mg capsules, by mouth, once daily, until radiographic or clinical progression (such as pathological fracture, cord compression, worsened pain requiring radiation therapy, or opioid analgesic dose increase or initiation), or unacceptable toxicity. Per the Investigator's clinical judgment and with sponsor approval, patients may be allowed to continue enzalutamide until the next treatment is initiated. If another non-cytotoxic, non-investigational, antineoplastic agent is initiated after protocol-defined progression has been determined, enzalutamide may be continued per the Investigator's clinical judgment and with sponsor approval as long as the patient is tolerating enzalutamide and continues androgen deprivation therapy.

The consensus guidelines of the Response Evaluation Criteria in Solid Tumors (RECIST) 1.1 and the Prostate Cancer Clinical Trials Working Group 2 (PCWG2) will be utilized to determine radiographic disease progression. Radiographic disease progression is defined by RECIST 1.1 for soft tissue disease. Bone disease progression is considered when a minimum of two new lesions are observed. Progression on bone scan at time points prior to or at week 9 requires a confirmatory scan performed six or more weeks later. This confirmatory

scan should demonstrate at least 2 additional new lesions compared to the Week 9 scan (PCWG2).

The following assessments of prostate cancer status will be collected during the course of the trial: soft tissue disease on computed tomography (CT) scan or on magnetic resonance imaging (MRI), bone disease on radionuclide bone scans, and PSA.

Throughout the study safety and tolerability will be assessed by the recording of adverse events, monitoring of vital signs, physical examinations, and safety laboratory evaluations.

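### The SAP's TEAE summaries do not separate events before and after an antineoplastic agent is added to enzalutamide

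*SAP*

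**What the plan says.** **Continuation with an added agent is planned.** Protocol 5.1.5 covers the addition of a further cancer drug that is neither cytotoxic nor under investigation. Once such a drug has been "initiated after protocol-defined progression has been determined, study drug therapy may be continued per the Investigator's clinical judgment and with sponsor approval", provided the patient tolerates enzalutamide and stays on androgen deprivation. SAP 3.2 repeats this: "If another non-cytotoxic, non-investigational, antineoplastic agent is initiated after protocol-defined progression has been determined, enzalutamide may be continued". The synopsis, Protocol 2.2.1 and the schedule footnotes say the same. Footnote b to Protocol Table 1 keeps adverse event and laboratory assessments at the Safety Follow-Up visit "regardless of initiation of another antineoplastic therapy prior to last dose of enzalutamide", and footnote j does the same for adverse event collection.

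**The TEAE window has no cut.** Under SAP 6.2 a TEAE is any adverse event after first dose, and "All adverse events collected that begin within 7 days after taking the last dose of study drug will also be counted as TEAE". A drug-related TEAE is "any TEAE with at least possible relationship to study treatment as assessed by the investigator or with missing assessment" of causality.

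**The summaries have no cut.** SAP 7.5.1 tabulates TEAEs by system organ class and preferred term, grade, seriousness, relatedness and discontinuation, with further tables limited to "common TEAEs that equal to or exceed a threshold of 5.0" per cent. SAP 7.8 defines subgroups for efficacy endpoints only, and SAP 7.9 plans no other analyses. Duration of exposure (SAP 6.5) runs from first to last dose.

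**The concern.** A secondary objective is the safety of enzalutamide re-treatment after chemotherapy. Once a second antineoplastic agent is on board, a new adverse event may come from enzalutamide, the added agent, their combination or the progressing cancer. The combination period starts after progression, and Protocol 5.5.2 states that "Clinical signs and symptoms due to disease progression will be collected as AEs". A single pooled table cannot show a reader which events arose before any added agent.

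The efficacy side of the SAP already makes this separation. rPFS (6.1.1), time to PSA progression (6.1.2) and composite PFS (6.1.4) are each censored when new anti-cancer therapy comes before the event. The safety tables have no counterpart.

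A secondary wording point concerns two places in the protocol. Section 6.1 lists a decision to start new anti-neoplastic therapy among the events that lead to removal from enzalutamide. The second-to-last sentence of 5.1.3.2 (repeated in the synopsis and Appendix 12.1) bars new systemic prostate cancer therapy on study. Neither mentions the exception in 5.1.5.

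**Working it through.** The point is about definitions, so the main check sets the rules side by side.

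1. *Can an event after the added agent be a TEAE?* Yes. The agent may start while enzalutamide continues (Protocol 5.1.5), adverse events are still collected (Table 1 footnotes b and j), and the window closes only 7 days after the last enzalutamide dose (SAP 6.2).
2. *Does any planned summary separate such events?* No. SAP 7.5.1, 7.8 and 7.9 contain no split at subsequent therapy.
3. *Do the relatedness tables do it indirectly?* In part. In Protocol 5.5.5 the 'Not Related' category covers events for which other drugs or underlying disease are plausible explanations, so an investigator can attribute an event to the added agent. But 'Possible' covers an event that "could also be explained by concurrent disease or other drugs or" chemicals, and SAP 6.2 counts both 'Possible' and missing causality as drug-related.
4. *Is the splitting date available?* Yes. Time to first subsequent antineoplastic therapy (SAP 6.1.2) already needs the start date of the first systemic agent.

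**Size.** The plan gives no figure for this point. Its nearest design figure, approximately 34 rPFS events (SAP 4), reproduces. With λ = ln 2 / 4 = 0.1733 per month, 12-month uniform accrual, 12-month minimum follow-up and 10% loss:

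40 × 0.90 × [1 − (e^(−12λ) − e^(−24λ)) / (12λ)] = 36 × [1 − (0.1250 − 0.0156) / 2.079] = 34.1.

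So most subjects are expected to progress or die, but this says nothing about how many will continue enzalutamide with an added agent.

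The following is illustration only, and every input is assumed. Let a TEAE affect b = 20% of 40 subjects (8) before any added agent. Let k subjects add an agent, and let the event newly arise in a fraction q of those still free of it. If adding an agent is unrelated to having had the event, pooled incidence = b + (k/40)(1 − b)q.

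| k | q = 10% | q = 30% |
|---|---|---|
| 2 | 20.4% (8.2 subjects) | 21.2% (8.5) |
| 4 | 20.8% (8.3) | 22.4% (9.0) |
| 10 | 22.0% (8.8) | 26.0% (10.4) |
| 16 | 23.2% (9.3) | 29.6% (11.8) |

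With 2 subjects the shift is at most half a subject; with 16 it can approach 4.

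The 5.0% threshold is a poor yardstick. It equals 2 subjects for a safety set of 36 to 40 (0.05 × 36 = 1.8, rounded up; 0.05 × 40 = 2). However, SAP 7.5.1 also tabulates all TEAEs with no threshold, so crossing it neither hides nor reveals an event.

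**The case against.** The strongest reply is that nothing here is an error. First dose to last dose plus 7 days is an ordinary on-drug window, and continuation with an added agent is part of the protocol's own regimen. **This stands**: the overall tables are valid for what they describe and should be kept.

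Second, other outputs help. Investigators can rate an event 'Not Related'. Protocol 7.5.1 lists all adverse events, and listings show recorded dates, so in a 40-subject study a reader could place most events by hand. **This stands in part.** The relatedness rule leaves ambiguous events on the drug-related side, and listings give no incidence, denominator or exposure by period.

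Third, few subjects may qualify. Continuation requires protocol-defined progression, a non-cytotoxic and non-investigational agent, sponsor approval and tolerance of enzalutamide. **This stands** as a limit on weight, since the documents give no count in either direction.

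Fourth, a time split is itself imperfect. Protocol 5.1.5 also allows enzalutamide alone after progression until the next treatment begins, so progression symptoms can fall in both periods. **This stands**, and the new summary should say so.

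On the wording point, the prohibited-medication list in 5.1.3.2 applies only before progression, and 5.1.5 is specific and needs sponsor approval. The intended reading is therefore clear enough.

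**Conclusion.** The point holds as a cheap improvement to a valid but pooled safety summary. It is minor. The SAP should let a reader see TEAEs before any added antineoplastic agent apart from those that follow one, because the secondary objective is about enzalutamide re-treatment. How much the pooled figures would move cannot be estimated from the documents, and the effect is negligible if few subjects continue with an added agent.

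A reader might infer three stronger things that the documents do not support.

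- *That the TEAE tables are wrong or overstate enzalutamide's toxicity.* They are correct as an all-on-drug summary, and no count of affected subjects or event rate is given from which to show a material distortion.
- *That splitting by time would establish cause.* It would not, because both periods can contain post-progression symptoms.
- *That Protocol 6.1 makes approved continuation a deviation.* Read literally, it could lead to coding under PD2 (withdrawal criteria met but subject not withdrawn). But Protocol 8.1.6 describes deviations as generally unplanned, and this continuation is planned and approved. At most it is a possible miscoding in one descriptive table.

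No analysis set, sample size or primary result depends on any of this.

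**What to change.** **SAP 7.5.1, before database lock.** Keep the overall TEAE tables and add one summary:

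- *Before any added agent:* TEAEs with onset before the start of the first subsequent systemic antineoplastic agent. The denominator is the whole SAF, with exposure days for that period.
- *After an added agent:* TEAEs with onset on or after that start, only for subjects who took at least one enzalutamide dose on or after the agent's start date, with their overlap exposure days.
- *Listed separately:* TEAEs in subjects who switched to a new agent within 7 days after their last enzalutamide dose, since they were never on the combination, and adverse events whose onset cannot be placed relative to the start date.
- *A note to the table:* both periods can include symptoms of progression, so the split does not prove cause.

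The cost is one derived flag and one table, with no new data.

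**Protocol, at the next amendment.** Add 'except as permitted in Section 5.1.5' to the 6.1 bullet on new anti-neoplastic therapy. Add it also to the sentence barring other new systemic therapy in 5.1.3.2 (the second-to-last sentence), the synopsis and Appendix 12.1. These are four small edits that need amendment sign-off, so they do not justify an amendment of their own.
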